9.5.3 Control of Type I Error

The primary null hypothesis will be tested at two-sided $\alpha = 0.05$. If, and only if, the treatment group comparison is statistically significant, the secondary hypotheses will be tested.

The 3 key secondary endpoints to be considered for study-wise type I error control are:

- Annualized flare rate for treated, AC-determined flares during the RCP.
- The proportion of subjects achieving flare-free, treatment-free complete remission at Week 52, defined as the lack of evident disease activity at Week 52, no AC-determined flare during the RCP, and no treatment for flare or IgG4-RD disease control except the required 8-week GC taper. Lack of evident disease activity is defined as either an IgG4-RD Responder Index (Wallace) score of 0, or a determination by the investigator that no disease activity is present based on physical, laboratory, pathology or other evidence.
- The proportion of subjects achieving flare-free, corticosteroid-free complete remission at Week 52, defined as the lack of evident disease activity at Week 52, no AC-determined flare during the RCP, and no corticosteroid treatment for flare or disease control except the required 8-week GC taper.

Null hypotheses for the three key secondary endpoints will be tested using Hochberg procedure (Hochberg, 1988). If the largest p-value is < 0.05, the null hypotheses for all three secondary endpoints will be rejected. If the largest p-value is ≥ 0.05 and the second largest one is < 0.025, the null hypotheses corresponding to the two endpoints with smaller p-values will be rejected. If the largest p-value is ≥ 0.025 , and the smaller p-value is ≥ 0.05 , the second largest one is ≥ 0.025 , and the smallest p-value is ≥ 0.05 , the second largest one is ≥ 0.025 , and the smallest p-value is ≥ 0.05 .

< 0.0167, only the null hypothesis corresponding to the endpoint with the smallest p-value will be rejected. Otherwise, no null hypothesis will be rejected.

9.5.4 Subgroup Analyses

Consistency of treatment effect measured by primary and 3 key secondary endpoints in the following subgroups will be investigated for the Full Analysis Set:

- Age (< 65 vs \ge 65)
- Sex (male vs female)
- Region (US vs non-US; EU vs non-EU; and Asia vs non-Asia)
- Serum IgG4 concentrations at baseline
- Racial/ethnic subgroups as needed for national/regional regulatory filings
- First or subsequent treatment course for IgG4-RD

The nominal p-value and 95% CIs of treatment effect will be provided for each subgroup analysis. Forest plots will be generated to visually present the consistency of treatment effect in different subgroups with overall treatment effect.

9.5.5 Safety Analysis

Safety endpoints will be summarized separately for the RCP, OLP and SFUP. Safety data from the RCP and OLP will be presented based on the Safety Analysis Set and on the Open-label Analysis Set, respectively. Data after subjects receive inebilizumab will be analyzed based on the Any Inebilizumab Analysis Set.

AE and SAE collection begins after the subject signs the informed consent document and lasts until the end of study visit. AESI identification will be based on MedDRA coding. The search criteria for the AESIs will be established prior to database lock for the primary analysis.

The number and percentage of subjects reporting TEAEs and TESAEs will be summarized for each treatment group by system organ class and preferred terms, by severity, and by relationship to the IP. The rate of AEs per 100 person-years at risk, calculated as (total number of AEs)/(total person years) \times 100, will also be reported.

AEs and SAEs collected during the RCP will be analyzed using a treatment policy strategy, (which includes all data captured during the RCP) and a while-on-treatment strategy (which includes all data captured while subjects are on treatment). The risk difference and corresponding 95% CI will be presented. In addition, the time to first instance of an AESI and duration of the AESI will summarized by treatment group when appropriate.

Clinically important abnormalities in vital signs, laboratory parameters, ECGs, and physical examinations will be recorded as AEs or SAEs. Laboratory measurements, as well as their changes from baseline at each collection time point and shift from baseline, if applicable, will be summarized descriptively.

Safety subgroup analyses will be investigated when appropriate and may include analyses by age (< 65 vs \geq 65), sex (male vs female), region (US vs non-US; EU vs non-EU; and Asia vs

Clinical Study Protocol VIB0551.P3.S2 - MITIGATE Amendment 9.1, 08AUG2023

non-Asia), serum IgG4 concentrations at baseline, stratification factor, and subgroups as needed for national/regional regulatory submissions.

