3.2 Secondary Objectives and Endpoints

Secondary Objectives

- To evaluate the safety and tolerability of inebilizumab in patients with IgG4-RD.
- To evaluate the effect of inebilizumab on other measures of disease activity.

Secondary Endpoints

- Annualized flare rate for treated and AC-determined flares during the RCP.
- The proportion of subjects achieving flare-free, treatment-free complete remission at Week 52, defined as the lack of evident disease activity at Week 52, no AC-determined flare during the RCP, and no treatment for flare or disease control except the required 8-week GC taper. Lack of evident disease activity is defined as either an IgG4-RD Responder Index (Wallace) score of 0, or a determination by the investigator that no disease activity is present based on physical, laboratory, pathology or other evidence.
- The proportion of subjects achieving flare-free, corticosteroid-free complete remission at Week 52, defined as the lack of evident disease activity at Week 52, no AC-determined flare during the RCP, and no corticosteroid treatment for flare or disease control except the required 8-week GC taper. Lack of evident disease activity is defined as either an IgG4-RD Responder Index (Wallace) score of 0, or a determination by the investigator that no disease activity is present based on physical, laboratory, pathology or other evidence.

- Time to initiation of first treatment (medication or procedure) for new or worsening disease activity by the Investigator within the RCP, regardless of AC determination of flare.
- Annualized flare rate for AC-determined flares, whether or not treated, during the RCP.
- Glucocorticoid use, calculated as the cumulative GC dose taken for the purpose of IgG4-RD disease control during the RCP.
- Incidence of TEAEs, TESAEs, and treatment-emergent adverse events of special interest (AESIs) during the 52-week RCP and during the OLP.
- The incidence of ADAs directed against inebilizumab during the RCP.

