#### **3.6.1** Adverse Events

Adverse event and serious adverse event collection begins after the subject signs the informed consent document and continues until the end of study visit. AEs and SAEs collected during the RCP will be analyzed using a treatment policy strategy (which includes all data captured during the RCP), and a while-on-treatment strategy (which includes all data captured while subjects are on treatment). AEs and SAEs collected during the OLP, SFP and combined RCP and OLP, will be analyzed using a treatment policy strategy. For subjects who withdraw from the study, data collected up until the last visit will be included. Table 5 defines TEAEs for different analyses.

RCP (Treatment Policy)	RCP (While-on- treatment)	OLP	Combined RCP and OLP (Any Inebilizumab Analysis Set)	SFP
A TEAE is defined as any AE with onset date on or after the first RCP IP dose, and on or before the end of RCP.	A TEAE is defined as any AE with onset date on or after the first RCP IP dose, and on or before 6 months (183 Days) after the last RCP dose.	A TEAE is defined as any AE with onset date on or after first OLP IP dose and up to the end of OLP (prior to the SFP entry if a subject enrolled into SFP).	A TEAE is defined as any AE with onset date on or after the first inebilizumab dose (either RCP or OLP) and up to and including the day prior to the end of RCP (if a subject didn't enroll into OLP) or the end of OLP (i.e., the day prior to the SFP entry, if a subject rolled over to OLP).	TEAE is defined as any AE with onset date after the last IP dose during the study.

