#### **Table 5 Definition of TEAEs for Different Analyses**

An adverse event of special interest (AESI) is one of scientific and/or medical interest specific to understanding safety and action of the IP. The following are considered AESIs in this study:

- Anaphylaxis and serious hypersensitivity reactions
- Infusion-related reactions (IRR)
- Immune complex disease
- Cytopenia
- Serious and/or opportunistic infections, including Progressive Multifocal Leukoencephalopathy (PML).

The AESIs (investigator reported) will be summarized by Category and PT. The risk difference and corresponding 95% CI calculated by the Miettinen and Nurminen score method in cumulative incidences of AESIs by week 52 between inebilizumab and placebo groups may be presented as appropriate. In addition, the time to first instance of an AESI and duration of the AESI will be summarized by treatment group when appropriate.

In addition, following sponsor identified AESIs will also be summarized: IRR, anaphylaxis, serious hypersensitivity reactions, immune complex disease, cytopenia, serious infections, and opportunistic infections. The detailed definition of sponsor identified AESIs will be included in the statistical programming plan (SPP).

AEs will be coded to the corresponding system organ class (SOC) and preferred terms (PT) using the most recent version of the Medical Dictionary for Regulatory Activities (MedDRA). In addition, summary of AEs and SAEs by SOC and FDA Medical Query (FMQ) will also be provided for RCP and the combined period of RCP and OLP.

The number and percentage of subjects reporting TEAEs and TESAEs will be summarized for each treatment group by SOC and PT, by severity, and by relationship to the IP. If the same AE occurs multiple times within a particular subject, the highest severity and level of relationship observed will be reported.

TEAEs and TESAEs will be summarized as described in Table 6.

TEAEs per 100 Person-years for a specific reporting period will be calculated as

$$= 100 \times \frac{\text{Total number of TEAEs for specific reporting period}}{\text{Total Person years for specific reporting period}}$$

The person-year for while-on-treatment analyses will be defined as (Date of 6 months [183 Days] after the last RCP dose - 1st RCP dose date +1)/365.25. See Table 4 for the definition of person-years for other analyses.

Overall summary of TEAEs
TEAEs by SOC and PT
TEAEs with severity $\geq$ Grade 3 by SOC and PT

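### The SAP has no pre-specified risk difference for TEAEs and TESAEs, although the protocol says one will be presented with its 95% CI

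*Protocol*

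**What the plan says.** Protocol 3.2 lists one secondary safety endpoint with three incidence components: "Incidence of TEAEs, TESAEs, and treatment-emergent adverse events of special interest (AESIs) during the 52-week RCP and during the OLP". SAP Table 1 repeats it.

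Protocol 9.5.5 begins the relevant paragraph with "AEs and SAEs collected during the RCP will be analyzed using a treatment policy strategy" and adds a while-on-treatment strategy. The next sentence is "The risk difference and corresponding 95% CI will be presented". AESIs come only after that: "In addition, the time to first instance of an AESI and duration of the AESI will summarized by treatment group when appropriate".

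SAP 3.6.1 keeps the sentence on the two strategies for RCP AEs and SAEs ("and a while-on-treatment strategy (which includes all data captured while subjects are on treatment"), but no risk-difference sentence follows it. The SAP's only safety risk difference appears later in the same section, by the Miettinen-Nurminen score method, "in cumulative incidences of AESIs by week 52 between inebilizumab and placebo groups may be presented as appropriate". For the other two components the SAP says "The number and percentage of subjects reporting TEAEs and TESAEs will be summarized for each treatment group by SOC and PT", with breakdowns by severity and relationship, and it adds event rates per 100 person-years. SAP 3.1 classes the while-on-treatment safety analyses as sensitivity analyses.

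**The concern.** The SAP differs from the protocol in two ways. The scope is narrowed from AEs and SAEs to AESIs, and a firm commitment becomes an option. The SAP's revision history mentions changes to key secondary endpoints, multiplicity and analysis windows, and added clarifying detail. It does not mention this change. An analyst who follows the SAP will produce no comparative estimate for TEAE or TESAE incidence.

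This matters because the trial is placebo-controlled with about 80 subjects per arm. At that size, two percentages side by side can be read as showing no excess when the data could not exclude a sizeable one. Protocol 2.1.5.3 shows how natural that reading is: it calls TEAE rates of 71.8% and 73.2% in the NMOSD study balanced. An interval shows directly how much uncertainty surrounds such a comparison.

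**Working it through.** **Comparison of the texts**

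- Event class. In the protocol, the sentence before the risk difference concerns RCP AEs and SAEs, and AESIs enter only afterwards as an addition. The natural antecedent is AEs and SAEs. In the SAP the risk difference covers AESIs only.
- Strength. The protocol's risk-difference sentence is unconditional, while the AESI sentence that follows it carries its own qualifier. The protocol therefore used a conditional phrase where it wanted one. The SAP's risk difference is optional.
- Strategy. The protocol sets out both strategies in the sentence before, and the risk-difference sentence does not repeat them. The SAP does not say which strategy its AESI risk difference uses.
- Period. The endpoint also covers the OLP, where everyone receives inebilizumab. A randomized comparison applies to the RCP only.

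**Arm size**

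Protocol 9.3 gives 39 flares and 160 subjects. Schoenfeld's formula gives 4 × (1.96 + 1.2816)² / (ln 0.35)² = 38.1, so 39 events. The average failure probability is (0.35 + 0.140)/2 = 0.245, and 39/0.245 = 159.2, so 160 subjects, or 80 per arm. The plan's figures reproduce. The concern itself rests on no stated figure.

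**Illustrative precision**

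The event rates are an assumption taken from the NMOSD study's randomized period (Protocol 2.1.5.3):

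- TESAEs 4.6% versus 8.9%: 0.046 × 80 = 3.7 and 0.089 × 80 = 7.1, rounded to 4 and 7.
- TEAEs 71.8% versus 73.2%: 0.718 × 80 = 57.4 and 0.732 × 80 = 58.6, rounded to 57 and 59.

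The Miettinen-Nurminen limits are the values of d that solve

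(p1 − p2 − d) / √{[q1(1 − q1)/n1 + q2(1 − q2)/n2] × N/(N − 1)} = ±1.96,

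where p1 and p2 are the observed proportions, q1 and q2 are the maximum-likelihood proportions under the constraint q1 − q2 = d, n1 = n2 = 80 and N = 160.

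- TESAE: 4/80 − 7/80 = 5.0% − 8.75% = −3.75, shown as −3.8 points. The limits are −12.7 and +4.7.
- TEAE: 57/80 − 59/80 = 71.25% − 73.75% = −2.5 points. The limits are −16.3 and +11.4.

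As a sensitivity check on the assumed rates, SAE counts of 14 versus 10, which have no source in the documents, give +5.0 points (−6.3 to +16.5). Counts of 8 versus 12 give −5.0 points (−15.8 to +5.6).

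**The case against.** The strongest defence is that the protocol's risk-difference sentence names no event class, level, method or strategy, and that Protocol 9.1 leaves further statistical detail to the SAP. The SAP also keeps the protocol's order, with the risk difference first and AESI timing and duration next, so its authors may have read the sentence as being about AESIs. The documents do not settle whether this was a reading or a deliberate reduction. In either case, the sentence before it concerns AEs and SAEs, and leaving out a stated analysis is more than filling in detail. The general line in SAP 3.1 on model-based estimates specifies no contrast for TEAEs or TESAEs.

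Several stronger readings are tempting, and the documents do not support them:

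- *Two secondary endpoints are lost.* TEAE and TESAE incidence are two of three components of one listed endpoint, and the third keeps an optional contrast.
- *The protocol expressly requires the risk difference under both strategies.* That is a fair inference from adjacent sentences, but it is not stated.
- *SAP Table 6 proves the omission because no row is a difference.* Its rows name displays and not the statistics in each, and a risk difference would be a column. The evidence is the SAP's prose.
- *The choice will be made after unblinding.* The SAP does not say when its optional wording is resolved, and that wording concerns AESIs only.
- *The information is lost.* Per-arm numbers are reported, so anyone can calculate a difference and an interval.

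It is also true that safety lies outside the multiplicity scheme, that no safety hypothesis test is planned, and that no efficacy conclusion depends on this point.

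**Conclusion.** The two documents conflict. The protocol says a risk difference with 95% CI will be presented, and its context is RCP AEs and SAEs. The SAP specifies none for TEAEs or TESAEs and makes the AESI one optional, with no recorded reason. The loss is limited to the promised, pre-specified between-arm estimate for two components of the secondary safety endpoint.

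Under the NMOSD-study rates, the intervals that would go unreported run about 8 to 9 points either side of the estimate for TESAEs and about 14 for TEAEs. Data that look balanced would still be compatible with an excess of about 5 points in TESAEs and about 11 in TEAEs. These sizes assume 80 per arm and rates carried over from another disease and a 28-week period. A 52-week trial in IgG4-RD may see different rates. The conflict does not depend on them.

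This is a consistency correction that should be made. It does not threaten the primary analysis.

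**What to change.** In SAP 3.6.1, state that the risk difference (inebilizumab minus placebo) with a Miettinen-Nurminen 95% CI will be presented for the RCP for subjects with any TEAE, any TESAE and any AESI. Present it under the treatment-policy strategy and, as the sensitivity analysis, while-on-treatment. Label the intervals descriptive and unadjusted. Replace the optional AESI wording ("between inebilizumab and placebo groups may be presented as appropriate") with a firm commitment. If the narrower scope was intended, amend Protocol 9.5.5 instead and record the reason.

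Risk differences for Grade 3 or higher events, IP discontinuation and individual preferred terms are optional, since the protocol does not call for them. If preferred terms are added, the existing 5% threshold in SAP Table 6 selects on the inebilizumab arm alone and would miss events that are commoner on placebo.

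The cost is SAP wording and extra columns in RCP tables, using a method the SAP already names and no new data. The downside is a few more unadjusted intervals.

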9.5.7 Immunogenicity Analysis

ADA will be summarized using descriptive statistics for each population. Number and percentage of subjects who developed positive ADA will be summarized by treatment group. The potential impact of ADA on the safety and efficacy of inebilizumab may be explored if data allow.

10 ETHICAL CONSIDERATIONS

10.1 Good Clinical Practice

The study will be performed in accordance with ethical principles that have their origin in the Declaration of Helsinki and are consistent with International Council for Harmonisation (ICH)/Good Clinical Practice (GCP), the European Union (EU) Clinical Trials Regulation No 536/2014 and applicable local and regional regulatory requirements.

10.2 Ethics Review

The final study protocol, including the final version of the ICF, must be approved or given a favorable opinion in writing by an IRB or IEC, as appropriate. The Investigator must submit written approval to Sponsor or representative before he or she can enroll any patient into the study.

The PI is responsible for informing the IRB or IEC of any amendment to the protocol in accordance with local requirements. In addition, the IRB or IEC must approve all advertising

Clinical Study Protocol	Horizon Therapeutics Ireland DAC
VIB0551.P3.S2 - MITIGATE	Inebilizumab
Amendment 9.1, 08AUG2023	IgG4-Related Disease

used to recruit subjects for the study. The protocol must be re-approved by the IRB or IEC upon receipt of amendments and annually, as local regulations require. The PI is also responsible to adhere to requirements stipulated by the respective IRB/IEC and for providing the IRB/IEC with reports of any reportable serious adverse drug reactions from any other study conducted with the IP. Sponsor will provide this information to the PI.

Progress reports and notifications of serious adverse drug reactions will be provided to the IRB or IEC according to local regulations and guidelines. Copies of all correspondence between the Investigator and the IRB/IEC is provided to Sponsor's representative.

In Japan the head of the study site should submit a notification of direction/determination, as well as IRB written approval, to the Sponsor and the Principal Investigator before enrollment of any subject into the study.

10.3 Informed Consent

The Investigator or other study site designee with IRB/IEC-approved qualifications will ensure that the patient is given full and adequate oral and written information about the nature, purpose, possible risk, and benefit of the study. Patients must also be notified that they are free to discontinue from the study at any time. The patients will be informed that their study record and medical records/documents that pertain directly to the study will be reviewed and possibly copied by Sponsor or its designee, or a governmental agency (such as the Food and Drug Administration [FDA]), and that every effort will be made to maintain patient confidentiality. The patient should be given the opportunity to ask questions and allowed time to consider the information provided.

The ICF must be witnessed and dated by the PI or his/her designee, and the original retained by the Investigator/study site as part of that subject's record.

The Investigator must maintain the original, signed ICF. A copy of the signed ICF must be given to the patient.

Patients may be rescreened within 30 days under the current and signed ICF.

The ICF must be fully approved by an IRB or an IEC prior to its use with study participants.

10.4 Deviation from the Clinical Study Protocol

The Investigator(s) must not deviate from or make any changes to the protocol without documented agreement between the Principal Investigator and the Sponsor or IRB/IEC approval, based on deliberations. This shall not apply to cases where the deviation or change is necessary to avoid an immediate hazard to the subjects, for other compelling medical reasons, or where the changes involve only logistical or administrative aspects of the clinical study (eg, changes to the organization/structure of Sponsor, the name/department of the study site, the address or phone number of the study site or Sponsor, or the job title of the Investigator or Medical Monitor). In such cases, the Principal Investigator must notify Sponsor, the head of the study site, and the IRB as soon as possible about the details of the deviation or change, the reason for the deviation, and a proposed revision in the protocol, if required, to obtain their approval.

For study sites in Japan, a certificate of approval by the head of the study site should be obtained via the head of the study site.

The Investigator(s) should document all deviations from the protocol regardless of the reason(s) or justification.

